- C Urine specimens collected for dipstick analysis during the screening visit are routine for patients with BPH and LUTS and will be handled according to standard of practice. The test results will be included in the subject's research and medical charts.

X. STATISTICAL ANALYSIS

The primary endpoint, change in AUASS score from baseline to 3 months, between the onaBoNT-A and tamsulosin groups will be analyzed using the 2-sided independent t-test.

Baseline measures of the data such as age and ethnicity as well as secondary endpoints will be examined using summary statistics to determine if any differences exist between the 2 study groups.

Graphical methods will be used to access distributional properties of the secondary endpoints (urinary flow rate, serum PSA, prostate volume symptom relief, post-void residual, BPH impact score, Bladder Function, Erectile Function and Ejaculatory Function questionnaires). If extreme departures from normality are found, use of non-parametric analytical methods such as the Wilcoxon rank-sum test or transformation of the data will be considered. Questionnaire scores will be examined for reliability using Cronbach's alpha. The distributions of the scores will be examined to see if they are evenly distributed around the mid-point of the scales or are clustered at the top or bottom of the scales (ceiling or floor effect). If strong ceiling or floor effects are found, this could limit the usefulness of these measures. Changes in these secondary endpoints will be assessed using either the independent t-test or its non-parametric equivalent, the Wilcoxon rank sum-test. Statistical analysis will be done using SAS, version 9.2 (SAS Institute, Cary NC).

The endpoints apoptotic index, proliferation index, nerve density, stromal reactive indexes, and vessel density, will be checked for their distributional properties using the methods described for the data collected in Aim 1. Change from baseline to 3 months will be analyzed using either the 2 sided t-test or the Wilcoxon rank sum test.

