Mean AUA score reduction in the alpha blocker group is expected to be at most 9.6 with a standard deviation of 6.3 based on published results of a randomized trial comparing tamsulosin versus placebo.²⁹ However, that same study showed a strong pill placebo effect with a mean reduction of 5.5, resulting in a treated reduction of 4.1 above the placebo group. Another study¹³, comparing botulinum toxin to placebo, showed a mean score reduction in the botulinum group of 15.2 and no placebo change. For our study, we will assume a mean reduction of 15.2 in the onaBoNT-A group which is 9.7 more than the pill placebo effect, a mean reduction of 9.6 in the alpha blocker group and a standard deviation of 6.3 for both groups. Based on these assumptions, a sample size of 29 subjects per group will achieve 90% power to detect a difference of 5.6 with an alpha level of 0.05 using the 2-sided independent t-test. Sample size calculations were done using PASS 2008 software (Hintze, J. (2008). NCSS, LLC. Kaysville, Utah. www.ncss.com).

The drop-out rate in the alpha-blocker study was as large as 20% and our own experience with onabotulinumtoxinA (onaBoNT-A) in the MIST-2 trial has demonstrated a dropout rate of 14%. So adjusting our sample size for an expected dropout rate of 20%, we will enroll 37 patients into the onaBoNT-A and tamsulosin groups for a total of 74 patients. To address some of the problems with possible attrition bias, we will use intent to treat analysis and patients will be kept in the study as long as possible even if they are no longer on treatment. We will also compare results between the intent to treat groups and the subjects who completed treatment to determine if differences exist.

XII. RETENTION AND DROPOUT/WITHDRAWAL

Minimal dropout or loss to follow-up is expected in this cohort, especially given the short follow-up. However, if a patient drops out before 4 weeks, he will be replaced so that the required sample size is realized. For purposes of tracking the feasibility of conducting a trial of treatment with onaBoNT-A, reasons for dropout or withdrawal will be documented.

XIII. CRITERIA FOR DISCONTINUING THE STUDY

- A Subjects unable to tolerate [tamsulosin or] onaBoNT-A due to side effects.
- B Subjects can request removal from the study for any reason at any time.
- C Subjects may be withdrawn at any time at the discretion of the investigator for safety, compliance, or other reasons.

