A discontinuation occurs when an enrolled subject ceases participation in the study, regardless of the circumstances, prior to completing the protocol.

The reasons for a subject discontinuing from the study will be recorded in the Case Report Form.

XIV. DATA ANALYSIS

Analysis will begin with descriptive statistics. Implausible and missing values will be identified and double-checked for accuracy. Parametric methodology will be used unless measurements have tested positive for violation of normality assumption. The differences between the study subjects groups will be evaluated using the paired-samples t-tests. The clinical outcomes will be compared using Fisher's test. The criterion for significance (alpha) has been set at 0.05. All tests are 2-tailed, which means that an effect in either direction will be interpreted. Analysis will be conducted using SPSS 17.0. ("SPSS Statistics 17.0", SPSS Inc., Chicago, IL, 2008).

XV. RISKS AND DISCOMFORTS

- A BOTOX®: It is expected that some participants may have some or all of the following side effects when given BOTOX®. Other side effects may occur which were not seen before. Side effects are usually temporary and manageable. However, it is possible they could cause serious disease or death. The study may include risks that are unknown at this time.

There have been rare reports of serious and/or immediate or even deadly abnormally sensitive reactions after treatment with BOTOX. These reactions include allergic reaction, skin rash, itching, swelling, and difficulty in breathing.

It is a rare possibility that the injection of BOTOX® could lead to botulism. The classic symptoms of botulism include double vision, blurred vision, drooping eyelids, slurred speech, difficulty swallowing, dry mouth, and muscle weakness. The doctor's examination may reveal that the gag reflex and the deep tendon reflexes like the knee jerk are decreased or absent.

There have been rare reports of sudden death, sometimes associated with difficulty in swallowing or pneumonia. There have also been rare reports of heart problems (including irregular heart beats and heart attack, some resulting in death). Some of these patients were already at risk for heart disease. It is not known if BOTOX actually caused these problems.

It should not be used when infection is present at the injection site or in people known to be abnormally sensitive to BOTOX.

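### The primary t-test on change in AUASS is valid but ignores the baseline score already collected, and Section XIV names a different, paired test for the group comparison

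*Combined protocol and SAP*

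**What the plan says.** Section X defines the primary analysis: "change in AUASS score from baseline to 3 months, between the onaBoNT-A and tamsulosin groups will be analyzed using the 2-sided independent t-test". Section XI sizes the trial for the same test, claiming "90% power to detect a difference of 5.6 with an alpha level of 0.05 using the 2-sided independent t-test" with 29 men per group. It assumes "a mean reduction of 9.6 in the alpha blocker group and a standard deviation of 6.3 for both groups", and a mean reduction of 15.2 on onaBoNT-A. Allowing for 20% dropout gives 37 per group, 74 in all.

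No covariate, ANCOVA or regression model appears in Sections X, XI or XIV. On baseline comparability, Section X says only: "Baseline measures of the data such as age and ethnicity as well as secondary endpoints will be examined using summary statistics". It states no action if a difference is found. For secondary endpoints, "Changes in these secondary endpoints will be assessed using either the independent t-test or its non-parametric equivalent". Randomization (Section VIII.A) is in blocks of 4, with no stratification described. The schedule of events (Section VIII.B) has the AUA symptom score at Visits 1, 6 and 7, so Visit 1 supplies the only pre-treatment value.

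Section XIV then says: "The differences between the study subjects groups will be evaluated using the paired-samples t-tests". It also names SPSS 17.0, where Section X names SAS 9.2. Nothing says which section governs.

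**The concern.** Subtracting baseline is the same as adjusting for it with a slope fixed at 1. When the true slope of the 3-month score on the baseline score is below 1, the subtraction over-corrects. That has two consequences, which are two views of one inefficiency:

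- The standard error is larger than it need be for the same men.
- In any one trial, part of a chance baseline imbalance stays in the estimate, in favour of the arm that started with the higher scores.

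This matters most if the true advantage is smaller than 5.6 points, and the protocol's own figures make that plausible. The 15.2-point reduction comes from a trial with a mean baseline of 23 (Section I), so it is about 15.2/23 = 66%. The Phase II trial in which this site took part saw AUASS improve by 39.1% and 42.6% at its two doses (Section II).

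The paired-test wording is a separate matter. Two parallel arms of different men have no pairs, so Section XIV cannot be applied as written to the comparison that Sections X and XI give to an independent t-test.

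**Working it through.** **The plan's own figure.** The inputs from Section XI are a difference of 15.2 - 9.6 = 5.6, SD 6.3 and two-sided alpha 0.05. The standard error at 29 per arm is 6.3 × √(2/29) = 1.65. The exact noncentral t gives 90.4% power at 28 per arm and 91.4% at 29, and 29/0.8 rounds up to 37. The plan's figures reproduce. At 29 per arm, the difference detectable with 90% power is 5.46 points.

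**Validity.** In 40,000 simulated null trials per setting (29 per arm, equal SDs, correlation 0.3, 0.5 and 0.7), the type I error was 4.8% to 4.9% for the t-test on change and 4.7% to 5.0% for ANCOVA.

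**Precision.** Let the baseline SD be s, the 3-month SD k·s and the correlation ρ. Neither ρ nor k is in the documents, so both are assumed. The SD of change is held at the plan's 6.3.

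- Variance of change: s²(1 + k² - 2ρk) = 6.3², which fixes s.
- ANCOVA residual variance: k²s²(1 - ρ²).
- Gross gain in effective patients: (variance of change ÷ residual variance) - 1.
- Cost of estimating the slope at n = 29 per arm: variance × (1 + 1/(2n - 4)) = 1 + 1/54 = 1.0185.
- Imbalance left in the change-score estimate after a baseline difference of one standard error: (1 - ρk) × s × √(2/29).

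Worked case, k = 1 and ρ = 0.5: s = 6.3; residual SD = 6.3 × √0.75 = 5.46; gross gain 1/0.75 - 1 = 33%; net gain 1.333/1.0185 - 1 = 31%. A one-standard-error baseline difference is 1.65 points, of which 0.5 × 1.65 = 0.83 remains.

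The three figures in each cell are for ρ = 0.3 / 0.5 / 0.7:

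| k (3-month SD ÷ baseline SD) | Gross gain, % | Net gain, % | Imbalance left, points |
|---|---|---|---|
| 0.8 | 99 / 75 / 59 | 95.6 / 71.8 / 56.4 | 1.17 / 1.08 / 1.01 |
| 1.0 | 54 / 33 / 18 | 51.0 / 30.9 / 15.5 | 0.98 / 0.83 / 0.64 |
| 1.25 | 28 / 12 / 2 | 25.2 / 10.0 / 0.1 | 0.77 / 0.54 / 0.23 |
| 1.4 | 19 / 6 / 0 | 16.7 / 4.2 / -1.8 | 0.66 / 0.40 / 0.03 |

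With equal SDs the residual SD is 5.08 / 5.46 / 5.81. The 90%-detectable difference, before the slope cost, is 4.40 / 4.73 / 5.03 against 5.46 unadjusted.

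**Power, net of the slope cost (noncentral t, 55 df, 29 per arm).**

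- For 5.6 points, the lowest value on the grid is 90.9% (k = 1.4, ρ = 0.7), against 91.4% for the planned test.
- For a true difference of 4.1 points, power is 74% to 85% at k = 1 and 68% to 78% at k = 1.25, against 68% unadjusted. The 4.1 is illustrative: in Section XI it is tamsulosin over placebo, not this trial's contrast.

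**The two sections side by side.** Sections X and XI both name the independent t-test for the AUASS comparison between arms. Section XIV assigns differences between the study groups to a paired test. It does not mention AUASS, but its wording is general and excludes nothing.

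**The case against.** The best reply is that nothing is broken. Endpoint, test and sizing agree between Sections X and XI, type I error holds, and residual imbalance is already reflected in the t-test's standard error. All of that is correct.

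The gain also rests on two undocumented quantities, and the grid includes zero and a small loss. The entry rule of AUASS above 8 truncates the baseline spread and could push k above 1, where the gain is smallest. A floor on follow-up scores could pull k back down. The documents do not settle this, and for that reason a range is shown.

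There may also be more slack than 29 per arm suggests. If all 37 per arm were analysed, the unadjusted test would have 96.5% power for 5.6 points and 78.9% for 4.1. That lowers the urgency, but the relative gain in precision is much the same at 37.

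Finally, the Visit 1 score may be taken while some men are still on an alpha-blocker, more than four weeks before injection. That is a fair caution about the baseline. It applies equally to the change score, which subtracts the same value, so it does not favour the t-test.

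The Section XIV wording is not rescued by any of these points.

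**Conclusion.** The point holds as a recommended improvement, together with a wording conflict that needs correcting in any case. The planned t-test is valid and adequately sized for 5.6 points. Adjusting for baseline is worth about 16% to 51% more patients net with equal SDs, 0% to 25% at an SD ratio of 1.25, and -2% to 17% at 1.4. These figures assume correlations of 0.3 to 0.7, a common slope, 29 evaluable men per arm and the plan's SD of change of 6.3. The worst case on the grid costs half a percentage point of power (91.4% to 90.9%). Confidence in the direction is good. Confidence in the size is moderate, because the correlation and the SD ratio are assumed.

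**What to change.** - **Section X:** pre-specify the primary analysis as an ANCOVA of 3-month AUASS (or, equivalently, change) on arm and baseline AUASS, with the Visit 1 score named as baseline. Report the adjusted difference with its 95% confidence interval. Keep the independent t-test on change as a sensitivity analysis.
- **Section X, exploratory:** report the arm-by-baseline interaction, because a single slope assumes that the effect does not vary with baseline.
- **Section X, secondary and tissue endpoints:** use the same adjustment where a baseline measure exists, on a transformed or rank scale if the data are skewed. No gain has been computed for these; the reason is consistency.
- **Section XI:** state that the t-test calculation is kept as the basis for sizing. The total of 74 need not change.
- **Section XIV:** replace the paired-samples wording for between-group differences so that it agrees with Section X, and name one software package.

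The cost is wording in three sections, one degree of freedom in the primary analysis, and a little extra programming for the exploratory and secondary analyses. It needs no extra patients, visits or data. The change should be fixed before unblinding.

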Transition zone biopsies will be performed at Visit 2, 30 days before treatment, and again at 3 months post-treatment. A total of 6 biopsy cores (i.e. 3 cores from the left and right transition zone) will be obtained from each volunteer. Prostate biopsy cores will be rapidly snap frozen in liquid nitrogen in coded and labeled containers and sent to [name] laboratory located at University of Texas Health Science Center - Houston Medical School for further processing.

A Randomization

Volunteers will be randomized using a blocked randomization approach by the MEDVAMC Research Pharmacy to either: ARM 1: onaBoNT-A 200 U prostate injection and placebo oral capsule daily or ARM 2: Placebo prostate injection (saline) and tamsulosin 0.4 mg capsule daily. Subjects will be randomized into one of the two treatment arms, using a block size of 4. The order in which the treatments are assigned in each block is randomized and this process is repeated for consecutive blocks of subjects until all subjects are randomized. This process ensures that after every fourth randomized subject, the number of subjects in each treatment group is equal. The MEDVAMC will prepare both pills (i.e. tamsulosin and placebo pill) and injections (i.e. onaBoNT-A and placebo saline injection) so that the study subject, investigator and all personnel treating or evaluating the subject will be blinded to treatment allocation.

B Schedule Of Events During Treatment Protocol

Tests/Time	Visit 1: Screening	Visit 2: Biopsy	Visit 3: Injection (4 weeks Post- biopsy ± 3 days)	Visit 4: Telephone Visit (Day 3 Post Prostate Injection)	Visit 5: Telephone Visit (1 Week Post- Injection ± 3 days)	Visit 6: (4 Weeks Post- Injection ± 3 days)	Visit 7: End of Study (3 months Post Injection ± 3 days)
Physical with DRE	X						X
Medical History	X						
Vital signs	X	X	X			X	X
Flowrate	X					X	X
PVR	X					X	X
PSA	X						X
CBC /platelet count	X						
Urinalysis (dipstick)	X	X	X			X	X
Biopsy(Transrectal Ultrasound Guided - TRUS)		X					X
Prostate Volume		X					X
Antibiotic		X	X				X
Fleets Enema		X	X				
Anesthesia (periprostate block)		X	X				
onabotulinumtoxin A or saline injection via TRUS			X				
Informed Consent	X						
Antibiotic dispensing	X	X				X	
Instructions to stop alpha blocker meds 7 days prior to biopsy	X						
Drug/Placebo dispensing			X			X	
Drug/Placebo accountability						X	X
AUA Symptom score	X					X	X
BPH Impact Scale	X					X	X
Bladder Function	X					X	X
Erectile Function	X					X	X

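### The comparison of ITT with treatment completers tells little about attrition bias, because neither set is defined and no method is stated for a missing 3-month AUASS

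*Combined protocol and SAP*

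**What the plan says.** Section X analyses "The primary endpoint, change in AUASS score from baseline to 3 months" with a two-sided independent t-test. Section XI states that "a sample size of 29 subjects per group will achieve 90% power to detect a difference of 5.6 with an alpha level of 0.05", and raises this to 37 per arm (74 in total) for 20% dropout.

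On losses, Section XI says: "To address some of the problems with possible attrition bias, we will use intent to treat analysis". It adds that men will be followed as long as possible after stopping treatment, and then: "We will also compare results between the intent to treat groups and the subjects who completed treatment to determine if differences exist". It defines neither the ITT set nor completion of treatment.

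Three other places bear on this:

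- **Section VIII.A:** Arm 1 receives "onaBoNT-A 200 U prostate injection and placebo oral capsule daily". Arm 2 receives a saline injection and a daily tamsulosin capsule.
- **Section XII:** a man who drops out before 4 weeks is replaced.
- **Sections XIII and XIV:** discontinuation means leaving the study before the protocol is complete, and missing values are to be identified and checked. No imputation, model or sensitivity analysis for missing scores is named.

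**The concern.** The t-test needs a 3-month score. With no rule for men who lack one, the most direct way to carry out the plan is to analyse the observed scores and call that ITT. Men lost before 3 months are then in neither the ITT result nor the completer result, and the two can agree however much the losses have shifted the treatment difference.

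The meaning of completion adds a second problem. The injection is given once, at Visit 3, and the only treatment left to complete is the capsule. Stopping it removes active drug in Arm 2 and only placebo in Arm 1, so the two completer groups are not selected alike.

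The risk is false reassurance about the primary result in a trial that expects one man in five to drop out.

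**Working it through.** **1. The plan's own figures.** Section XI says "we will assume a mean reduction of 15.2 in the onaBoNT-A group" and "a mean reduction of 9.6 in the alpha blocker group", with SD 6.3 in both arms. The difference is 15.2 − 9.6 = 5.6. With noncentrality 5.6 / (6.3 × √(2/n)) and two-sided alpha 0.05, exact power is 90.4% at n = 28 and 91.4% at n = 29 per arm. Dropout: 29 / (1 − 0.20) = 36.25, rounded up to 37. The stated 29, 37 and 74 reproduce.

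**2. What the check compares, by reading.**

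| ITT run on | Completed means | Men lost before 3 months | What a gap shows |
|---|---|---|---|
| Observed 3-month scores | Finished the protocol | Absent from both sides | Nearly the same men on both sides, so almost nothing |
| Observed 3-month scores | Finished the capsules | Absent from both sides | Effect of stopping the capsule among men still followed |
| All randomised, missing scores imputed | Either | In ITT, not among completers | Depends on the imputation, and the plan states none |

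**3. Losses that bias the result.** The loss pattern is assumed. Start with 37 per arm and lose the 7 tamsulosin men with the poorest week-4 response and 5 random onaBoNT-A men, leaving 30 and 32. Take week-4 and month-3 changes as bivariate normal with equal means and SDs and correlation r. The best 30 of 37 normal values average about 0.324 SD above the mean of all 37, so the remaining tamsulosin mean rises by r × 6.3 × 0.324 = 2.04r. The expected observed difference is 5.6 − 2.04r. Power is simulated.

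| r | Observed difference | Power |
|---|---|---|
| 0.5 | 5.6 − 1.02 = 4.6 | 82% |
| 0.7 | 5.6 − 1.43 = 4.2 | 76% |
| 0.9 | 5.6 − 1.84 = 3.8 | 70% |

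The comparator is random loss of the same numbers. At 32 and 30 men with a difference of 5.6, power is 93%. Regression imputation within arm from the week-4 score returns about 5.6 at all three correlations.

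**4. The opposite direction.** Suppose the 8 onaBoNT-A men with the poorest 3-month outcome and 8 random tamsulosin men are lost, an extreme pattern. The mean observed difference rises from 5.6 to 7.9. With no true difference, the two-sided rejection rate rises from 5% to about 35%.

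**5. A gap with no attrition.** Nobody is lost, and k of 37 men per arm stop the capsule but are followed. Assume men off tamsulosin average 5.5 (Section XI's pill-placebo reduction), men off the placebo capsule stay at 15.2, and completers average 15.2 and 9.6. The ITT difference is 15.2 − ((37 − k) × 9.6 + k × 5.5) / 37.

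| k | ITT difference | Gap from completers (5.6) |
|---|---|---|
| 2 | 5.82 | 0.22 |
| 4 | 6.04 | 0.44 |
| 8 | 6.49 | 0.89 |

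**The case against.** A reader might infer that the check can never reveal attrition bias, or that ITT and completer results must coincide exactly. The documents do not support that. They promise ITT without saying how a missing score is treated, and ITT could mean all randomised men with some imputation. If the week-4 score were carried forward in the scenario of step 3, the ITT difference would be about 6.4, 6.1 and 5.8, against 4.6, 4.2 and 3.8 in completers. That is a gap of roughly 2 points. An exact zero follows only if both sets are taken to be the men with a 3-month score.

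Nor do the documents say that completion turns on the capsule. That is a reasonable inference from a single injection, but the nearest definition, in Section XIII, concerns leaving the study. On that reading the capsule argument falls away.

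The plan also deserves credit for following men off treatment, its main protection against missing scores. Those men are in ITT and may not be completers, so the comparison can show an effect of stopping treatment. A completer analysis is common as support. Section XI claims only to address some of the attrition problem.

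Finally, the 96% power at 37 per arm with nobody lost is not a fair baseline, because the plan allowed for dropout.

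All of this limits the claim. It does not make the check informative about men who are lost, because the imputation that would do so is nowhere stated.

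**Conclusion.** The concern holds in a conditional form. As written, the only comparative check on attrition bias rests on two undefined sets and no missing-score method. Run on observed scores, it is silent about lost men. If completion means the capsules, it measures stopping tamsulosin. Only an ITT that imputes lost men would make it respond to losses.

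Under the main assumed pattern, the difference shrinks by 1.0 to 1.8 points and power drops by 11 to 23 points from 93%. Loss of poor responders from the other arm would inflate the difference instead. These sizes depend on the assumed losses and correlations, which the documents do not give; they show what the check could miss and do not forecast it. The replacement rule in Section XII adds to the problem: a man who leaves before 4 weeks has no post-baseline AUASS, and whether he stays in ITT is not stated.

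The planned primary test and sample size are not in question. This should be corrected before analysis.

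**What to change.** 1. Define ITT as all randomised men, including those who drop out before 4 weeks and are replaced.
2. Replace the attrition check with multiple imputation of the missing 3-month AUASS from arm, baseline and the week-4 AUASS already collected at Visit 6. For men lost before week 4, use arm and baseline only.
3. Add one missing-not-at-random sensitivity analysis, such as an arm-specific delta or a tipping point, and report the shift at which the conclusion changes. Other forms would serve; what matters is that one is stated in advance.
4. Keep any completer analysis as descriptive only. Define completion by the active component in each arm (Arm 1: injection received; Arm 2: capsules taken to Visit 7), and do not test it against ITT.

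The cost is revised wording, a few hours of programming and slightly wider intervals. No new data, visits or patients are needed.
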